The failure to use isoniazid (INH) preventative therapy (IPT) in HIV-infected individuals in Sub-Saharan Africa represents one of the single biggest implementation gaps between evidence and practice in today's response to the HIV epidemic. IPT reduces TB incidence by 40%.^{1,2} Yet today, in Africa, less than 2% of eligible individuals receive IPT³ and TB remains the largest killer of HIV-infected persons.⁴ Given the existence of both clear guidelines recommending IPT from international organizations and national health ministries in Africa, as well as simple symptom-based clinical algorithms for identifying persons eligible for IPT that can be applied by front line health care workers,⁵ a remaining critical requirement for IPT scale-up is strengthening the link – mediated by middle management in most health systems – between health ministry policy and clinics.

In the Republic of Uganda, the 112 local District Health Officers (DHOs) are the highest-ranking health officials based in the field and outside of the capital city, and serve as key middle managers working at the nexus between policy and implementation. In Uganda, <1% of eligible HIV-infected patients have initiated IPT.³ Our preliminary work has identified three barriers among DHOs to IPT uptake. First, knowledge of scientific evidence of the efficacy of IPT has not diffused among DHOs (and downstream to providers). Second, the system is already perceived as operating at capacity, and adding yet another two pills (INH and Vitamin B6) to prevent a long-term outcome is not prioritized. Third, geographic remoteness and poor infrastructure (e.g. roads and internet) dilute managerial efficacy and accountability between DHOs and the front line workforce.

To catalyze IPT implementation across Uganda, we propose to test a multi-component “SPIRIT” (Simplified INH Preventive Therapy) intervention targeting DHOs – whom we view as critical dissemination agents – in two geographical regions in Uganda. Our intervention is based on the empirically-validated PRECEDE model,⁶ which suggests that health promotion strategies are most effective when they combine: (1) “predisposing factors” comprised of knowledge, attitudes or beliefs that affect behavior; (2) “enabling factors” that facilitate change by making the behavior “easier”; and (3) “reinforcing factors” which include anticipated consequences following a behavior.⁷

[figure not shown]
The SPIRIT intervention therefore, first, convenes intervention groups of DHOs into mini-collaboratives to disseminate knowledge about efficacy of IPT and to predispose them towards deployment of IPT. Small-world network theory suggests that random links between mini-collaborative members will speed diffusion of this predisposing information and accelerate attitude change towards IPT within the group.⁸ Theories of social influence and persuasion suggest that, because of their authority and influence, attitude change among DHOs will result in changes in practice among the front line providers they oversee.⁹ Second, we will also deploy a two-way SMS system for DHOs and health care workers, based on local input and a behavioral construct, to facilitate communication between “hub” and “spoke.” Third, we will provide DHOs data on their district IPT uptake and share these data with their peers in the collaborative, thereby using a reputational approach to reinforce implementation of IPT.

1.1 Study Synopsis

We will evaluate the effect of the SPIRIT intervention on provider prescription and patient use of a 6-month course of IPT among all adults in HIV care in Uganda. SPIRIT is a multicomponent intervention based on the PRECEDE model of behavioral change targeted primarily at the level of the DHO. The SPIRIT intervention deploys predisposing (teaching collaborative); enabling (SMS); and reinforcing (reporting collaborative) components. The study design is a cluster randomized trial where the unit of randomization is a group of 4-6 DHOs: seven groups randomized to the intervention and seven to the current country standard of care. The primary endpoint of the study is the rate at which eligible HIV-positive adults (defined by the Ugandan Ministry of Health) receive a prescription for INH in health facilities overseen by DHOs participating in the SPIRIT trial. Secondary endpoints include: a) IPT completion measured through analyzing successful INH refill patient-visits; b) DHO and health worker attitudes towards IPT; c) TB incidence; d) DHO leadership and management skills and e) costing and cost-effectiveness. The overall goal of the proposal is to test the effectiveness of a scalable approach to increasing IPT uptake through a behavioral change model targeting DHOs (middle managers) within the Uganda health infrastructure. In a second phase of the trial (Phase 2: Years 4-5), we will: a) evaluate the impact of enhanced business management training, focused on SPIRIT intervention DHOs in

the Southwestern Uganda region, on IPT initiation in the region during Phase 2; and b) implement a training of trainers (ToT) curriculum among DHOs enrolled in the SPIRIT trial from the southwestern region of Uganda to determine if DHO-provided business management training of their District Health Team (DHT) members can improve the management skills of the DHT members. **Figure 1** provides a schematic overview of the SPIRIT study:

Figure 1. SPIRIT study schema. For illustration we show 10 DHO groups per arm with 5 DHOs per group. The trial will enroll 14 DHO Groups: 7 intervention and 7 control. In Years 4 and 5 (Phase 2), the trial will be limited to the 14 districts in the Southwestern region of Uganda.

1.2 Background & Rationale

Tuberculosis (TB) remains a major cause of death among persons living with HIV; yet, proven prevention strategies such as isoniazid preventive therapy (IPT) that can reduce TB by 40% are not being fully deployed.³ The data to support efficacy of IPT for TB prevention in HIV-infected adults are extremely robust.¹⁰⁻¹⁴ Randomized trials and cohort studies conducted in both high and low TB prevalence settings show that IPT reduces the incidence of active TB by approximately 40 percent,^{1,2} is safe to administer,^{13,15} and is not associated with an increase in isoniazid resistance among TB breakthrough cases.¹⁶ IPT provides independent protection against TB among persons receiving antiretroviral therapy (ART), even at high CD4 cell counts.¹⁷ In a recent post-trial extension study of a large randomized trial of IPT among HIV-infected adults with high CD4 cell counts in Africa, IPT recipients had significant reductions in mortality compared to IPT non-recipients, independent of ART.¹⁸ WHO guidelines recommend IPT for all persons living

with HIV (PLWHIV), regardless of the results of reactive tuberculin skin testing, a marker for highest TB risk.⁵ Yet despite these compelling data, the 2014 Global TB report showed that globally, fewer than 2% of PLWHIV in Africa are receiving IPT.³

Some of the reasons for poor uptake of IPT in Africa in the past - no country policy and lack of protocols for providers to rule out active TB disease - are no longer barriers. Based on data cited above, IPT is recommended for TB prevention by the WHO and at the country level. From a provider perspective, the inability to exclude active TB in IPT candidates (posing a risk for single drug treatment of undiagnosed active TB) has been a legitimate concern for the widespread uptake of IPT. However, there are now evidence-based country protocols for ruling out active TB supported by existing and new data,¹⁹ and from trials in HIV-infected patients with both high CD4 cell counts (TEMPRANO study)¹⁷ and low CD4 counts (REMEMBER study),²⁰ showing that simple clinical algorithms with or without the addition of new diagnostics, such as the Xpert MTB/RIF assay, can identify a high proportion of PLWHIV who are candidates for IPT.

A study of IPT implementation targeting the “middle managers” of the health system - the 112 District Health Officers (DHOs) responsible for public health in Uganda - is likely to have the highest impact at scale. Although the behavior of health care workers has often been the focus of implementation interventions, for public health interventions in which adoption at scale is a crucial goal, targeting the “middle managers” of the health system – the DHOs – may achieve a greater overall impact, because each DHO oversees budgetary, education and operational aspects of public health over a catchment area of >300,000 residents. In light of the heterogeneity in disease burden between districts, an intervention targeting DHOs vs a single intervention for all health providers in Uganda creates potential efficiency by influencing the highest level of regional authority and permitting flexibility for DHOs to facilitate implementation within their region.

Birken reports four major “points of influence” of a middle manager in a theoretical framework where health policy moves (or not) to implementation and effectiveness.²¹ These points of influence include 1) information diffusion; 2) synthesis of data; 3) day-to-day activity; and 4) “selling” of implementation. In designing SPIRIT, we used formative data to conceive of an intervention to overcome current barriers (real or perceived) to IPT implementation at the DHO level. The SPIRIT intervention is based on the PRECEDE model of behavioral change⁶ and exploits specific “points of influence” within the DHO’s role as middle manager. Some components of the intervention, such as making a single pill combination of INH/B6/septrin available, also serve as “enablers” for front line providers and patients for IPT uptake, thus mitigating the risk of reliance on one level of the health system in our intervention strategy.

Social network analysis assumes interpersonal connections rather than individual “rational agent” characteristics drive the spread of behaviors,²²⁻²⁶ including practice patterns of health care professionals. Sociologists have long observed that new ideas and practices – from adoption of contraceptives to new farming practices – spread through interpersonal contact.²⁷ The importance of interpersonal contact in dissemination extends, perhaps exquisitely so, to health care provider behavior. A seminal study in diffusion science from the 1950’s and still cited today found that opinion leaders in a community of physicians drove uptake of a new antibiotic through interpersonal contact.²⁸ Since then, numerous studies have documented the effect of social networks on issues ranging from reducing unnecessary caesarian sections to uptake of novel diagnostic and treatment strategies.²⁹⁻³² Although pharmaceutical companies commonly use network principles to influence drug sales,³³ public health research has not fully exploited these principles to promote dissemination of evidence-based interventions. The SPIRIT intervention will utilize the social networks of DHOs as an agent of behavioral change to catalyze IPT uptake.

The SPIRIT intervention incorporates contemporary understandings of relational influences on attitude change, namely that attitude change is motivated not only by absorption of new knowledge, but by normative concerns for ensuring coherent and favorable evaluations of the self (resolving cognitive dissonance, or a conflict between one’s knowledge and behaviors), and satisfactory relations with others given the rewards/punishments they can provide.⁹ We posit that DHOs will catalyze IPT uptake via their roles both as credible sources of clinical expertise for front line providers, and as key actors in health systems empowered with oversight (dispensing rewards and punishments e.g. hiring, firing, retrenchment) of providers. The SMS messaging component will facilitate the influence of DHOs via enhancing their communication with providers.

Examining cost-effectiveness and resource utilization of any intervention is critical to evaluate value and sustainability in an era where resources are being stretched to treat PLWHIV patients new to and already in care. Modeling studies support the investment in IPT as cost-effective.³⁴⁻³⁶ Preventing a TB case is not only cost saving in terms of potential mortality and downstream effects, but also in the morbidity associated with the disease. SPIRIT is designed to test an intervention that is intentionally “simple” by targeting DHOs, mobilizing existing systems, inserting IPT into ongoing ART care structures, and facilitating patient adherence via an SPC. However, there are costs associated with DHO training, introducing a new medication (the SPC INH/B6/septrin) on the formulary, as well as maintaining stocks of the SPC. Our proposal includes a specific costing domain that will measure these processes and provide useful information for countries considering using the SPIRIT strategy to achieve countrywide scale-up of IPT.

Scale up of IPT is long overdue, and research such as that proposed here is needed to assess how to effectively achieve roll out at the country level. Uganda is an ideal location for this study given: a) a high TB burden and large population of PLWHIV; b) government policies supporting IPT use in PLWHIV; c) DHO authority and residence within the community; d) high uptake of TB screening already achieved in ART clinics; and e) high level stakeholder “buy-in” for a sustainable IPT program. The benefit is clear: **Testing an intervention that could improve worldwide delivery of IPT for PLWHIV in high TB burden countries could dramatically reduce global morbidity and mortality from TB.**

2. Study Objectives

Aim 1: Determine if the SPIRIT intervention increases IPT initiation. We will form 14 groups of 4-7 District Health Officers and randomize half to the SPIRIT intervention and half to control (country standard) in a cluster randomized trial. The primary outcome will be the rate at which eligible HIV-infected adults receive a prescription for INH in health facilities overseen by DHOs participating in the SPIRIT trial. In all DHO groups the primary outcome will be measured over the 12-36-month period following the intervention initiation to account for INH stockouts and intervention start up time. We will use health information systems already in place to collect data about visits, IPT eligibility and IPT initiation. For secondary outcomes, we will conduct pre-/post-intervention surveys, focus group discussions, and key informant interviews to assess changes in knowledge, attitudes and practices regarding IPT among the DHOs and front line health workers in intervention and control groups, to assess mechanisms through which the intervention achieves outcomes.

Aim 2: Evaluate the effect of the SPIRIT intervention on IPT completion and TB incidence. Even if the intervention increases IPT initiation, quantifying actual use of IPT by patients and downstream effects on population health status (e.g. reduction in TB incidence) are important to assess impact and thereby enable policy makers to prioritize this intervention more widely. A subset of adult patients who received a prescription for IPT will be randomly sampled to measure IPT completion through patient chart review. TB incidence will also be measured on the overall population of HIV-positive adults in care at health facilities overseen by the DHOs.

Aim 3: Evaluate the impact of business training on leadership and management skills among SPIRIT intervention vs. control DHOs. At the completion of the 36-month period following SPIRIT intervention initiation, we will evaluate leadership and management skills, assessed by cross-sectional leadership and management survey measures, among SPIRIT intervention DHO groups who participated in business training within the SPIRIT intervention and control DHO group members.

Aim 4: Evaluate the cost and cost-effectiveness of SPIRIT. Using effectiveness measures obtained in Aims 1 and 2, and standard time and motion and costing methods, we will estimate the cost and cost-effectiveness of SPIRIT vs. standard of care in our sampled population from Aim 2. Outcomes of interest will include program costs per: a) IPT initiation b) IPT completion and c) TB case averted.

Aim 5: To evaluate the effect of enhanced business training among DHOs in the southwestern Uganda region on IPT initiation during years 4-5 of trial follow-up (Phase 2). Building on business training introduced within the SPIRIT intervention, we will provide additional management training (“Gap Analysis”) to a subset of SPIRIT intervention DHO groups, in the southwestern Uganda region, in order to evaluate the impact of enhanced business training on ongoing IPT initiation, at quarterly business training meetings.

Aim 6: To determine if having DHOs provide business leadership and management training to their District Health Teams (DHTs) can improve district-level management practices and health outcomes. We will implement a “training of trainers” (ToT) curriculum during Phase 2 of the trial, in which we will provide intervention group DHOs from Southwestern Uganda with training on how to provide business leadership and management training (modeled after the business training the SPIRIT intervention DHOs received in the first phase of the trial) to their DHT members. DHOs oversee and lead District Health Team members (i.e., assistant health officers and disease-specific focal persons) in addressing public health priorities for each district in Uganda. At the completion of Phase 2, we will determine whether DHO-provided training of DHTs impacted management practices and health outcomes at the district level, in districts in SPIRIT intervention vs. control DHO groups in the Southwestern Uganda region.

Our overall objective is to determine if a multi-component implementation intervention (SPIRIT) that targets DHOs can increase IPT initiation and completion among HIV-infected persons, and decrease TB incidence, as compared to country standard practices, in a cluster randomized trial in Uganda.

3. Study Site & Population

3.1 Study Setting

This study is evaluating the impact of the SPIRIT intervention on the implementation of IPT in two major geographic regions of Uganda: the Southwest, East and Eastern-Central regions (with the exception of Kampala and Wakiso (Kampala's surrounding suburb)). There are an estimated 1.5 million PLWHIV in Uganda.³⁷ Following ART scale-up over the last decade, Uganda's ART program, supported by a combination of PEPFAR funding (CDC and USAID), the Global Fund, the Ugandan government and other NGOs, now offers HIV care to 800,000 persons (~570,000 persons on ART) at 1,500 facilities. The MoH is the governing body of the Uganda Health System. The MoH is responsible for coordination and provision of technical guidance for the public health system; within the MoH, the AIDS Control Program coordinates service delivery in public and private facilities and public health programs. Within the MoH are District Health Officers (DHOs) who oversee health facilities and health budgets in their assigned districts (112 total in Uganda as of 2017) and bear overall responsibility for the training and oversight of providers and implementation of MOH policy. DHOs are responsible for coordination of various HIV Implementing Partners (IPs), including the Private not for Profits, and ensure that linkages and referral mechanisms between IPs and other district entities are functional in offering comprehensive services for HIV treatment and prevention.

3.2 Study Population

Aim 1: IPT Initiation: The target population for the SPIRIT trial intervention is DHOs, the DHOs' TB support staff, and the health facilities they oversee in the geographic regions participating in SPIRIT (the Southwest, East and East-central regions). The target population for the trial's primary outcome is all HIV+ adult (≥ 15 years) patients who are eligible for IPT by Uganda Ministry of Health Guidelines (in each pair-matched DHO group), and in care at a facility overseen by DHOs participating in the SPIRIT trial.

Aim 2: IPT Completion & TB Incidence: Adherence and TB incidence will be measured in a sub-sample of HIV+ adults prescribed IPT at a facility overseen by the DHOs (N=800), using patient chart review. TB incidence will also be measured among all HIV+ adults in care at health facilities overseen by the DHOs participating in the SPIRIT trial based MoH TB Registry entries.

Aim 3: The Aim 1 study population.

Aim 4: Cost and Cost-effectiveness: The study population for Aim 4 will be the sub-sample from Aim 2.

Aims 5 & 6: The target populations for the Phase 2 intervention period are DHOs and their respective District Health Team (DHT) members included in the training-of-trainers (ToT) curriculum and evaluation from the Southwestern Uganda region of SPIRIT. DHOs oversee all health aspects of a district and manage DHTs, comprised of a group of 6-8 health care professionals including the TB, HIV, Malaria and Laboratory focal persons, clinic in-charges, district biostatistician, and maternal and child health officer. The target population for Phase 2 leadership and management outcomes are the DHT members. The target population for Phase 2 health outcomes are district residents in the Southwestern region districts participating in the SPIRIT trial.

4. Study Design

The overall study design is a pair-matched cluster randomized trial. In Phase 1, the clusters correspond to groups of DHOs and are pair-matched within region on predictors of the primary outcome (IPT uptake). The primary outcome of IPT initiation as well as key secondary outcomes of IPT completion and TB incidence, and will be measured among providers and patients in facilities overseen by the DHOs. A sub-sample of adults prescribed INH will be followed longitudinally and assessed for adherence, TB incidence, and costing outcomes (Aims 2 and 4). In Phase 2, we will evaluate the impacts of enhanced business training among Phase 1 SPIRIT intervention DHOs from Southwestern Uganda on IPT initiation (Aim 5) and determine the effect of DHO-provided business training (following DHO participation in a training of trainers' curriculum) on the leadership and management skills of the District Health Team (DHT) members they supervise and health outcomes that DHTs oversee in Southwestern Uganda (Aim 6).

5. The SPIRIT Intervention Trial

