The primary outcome of IPT uptake is the rate at which eligible HIV-infected adults who receive a prescription for INH at a health facility overseen by DHOs participating in the SPIRIT trial. IPT initiation will be measured among the two largest clinics in each district and over the 24-month period, beginning 12 months after the intervention start in each pair-matched DHO group. The 12-month lead-in is to account for ramp-up of the SPIRIT intervention and for INH stock-outs. The denominator of this rate is the person-time-at-risk of starting IPT, accounting for prior starts and other changes in the active care population. The numerator is the number of HIV-infected adults prescribed INH. In other words, the primary outcome is the incidence rate of IPT prescriptions among eligible HIV-positive patients. The primary outcome will be compared between SPIRIT intervention and control groups.

Secondary outcomes will include:

1) Changes in DHO and providers’ knowledge and attitudes related to IPT in both intervention and control arms over time, as measured by quantitative surveys and data from focus group discussions (FGDs) within intervention districts and Key Informant Interviews (KII) within control districts. We will compare these changes across study arms.

2) In addition, for frontline providers, we will compare measures of social influence of DHOs on their own attitudes and practices in the intervention vs. control arms. These measures include perceptions of DHO credibility, salience of information from DHOs, and level of exposure to DHO influence (via assessment of quality and quantity of communications from DHOs).

3) Additional clinical secondary outcomes will include: a) IPT completion - as measured by sufficient INH refill visits to complete 180 doses of INH in a nine-month period, recorded on IPT registry or “blue card” clinical data from clinics overseen by DHOs participating in the SPIRIT cluster randomized trial; and b) TB incidence, as measured from government TB registry data from each district. We will compare these outcomes (IPT completion and TB incidence) by study arm, within the sub-sample described for Aim 2 (below).

The schedule of evaluation for outcome measures is shown in Table 2.

Table 2. SPIRIT Trial - Schedule of Evaluations

		Baseline	2-4 Months	6 Months	12 Months	18 Months	24 Months	30 Months	36 Months

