Primary outcome: We will examine the impact of the SPIRIT intervention on the incidence rate of TB among all HIV-positive adults at a health facility overseen by DHOs participating in the SPIRIT trial. The analysis of TB incidence in the population will mirror the primary analysis of Aim 1. Assuming an incidence rate 200 cases per 100,000 person-years in the standard of care,⁴⁵ and 10% completion of IPT (which conservatively reduces TB incidence by 40%,^{1,2} the incidence density method suggests a two-year cumulative incidence of approximately 0.38% in the control arm. Figure 4 shows the effect size that we are powered to detect when the control cumulative incidence is 0.35-0.40%.⁴⁴ Since the outcome is rare, these calculations are more sensitive to the number of patients per DHO group. However, we are relying on existing data collection systems (“blue card” forms and MoH TB clinic registries). Therefore, we anticipate capturing TB case reports on at least 3000 patients per DHO group. Assuming a control incidence of 0.38%, at least 2800 eligible patients in each DHO group, 12 DHO groups per arm, and a matched pair coefficient of variation $k_m=0.2$, we will be powered to detect 40% reduction in TB incidence in the overall population.

The analysis of TB incidence in the sub-sample of Aim 2 will mirror the analysis of IPT completion (Section 6.5.2.1). We will adjust for clustering and the sampling probability to make inferences about the target population of IPT-prescribed, HIV-infected persons in Uganda.

Figure 4: Effect size (in percent decrease in TB incidence) detected with at least 80% varying the incidence under the standard of care (SoC) and number of HIV-positive adults per DHO group. We assume 12 DHO groups per arm and a matched pair coefficient of variation $km=0.2$.

**Effect Size Detected with 80% Power
Varying the Number of HIV+ Adults
and TB incidence in the Standard of Care (km: 0.2)**

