8.1 Costs

We will use standard micro-costing techniques to measure the cost of each component of the SPIRIT intervention. This will include costing of training activities and efforts made to transfer knowledge to DHOs in meetings; costs associated with utilizing opinion leaders to teach DHOs; costs of the SPC for administering INH, SMS system development and implementation, and other communication efforts; and costs of biannual meetings held with DHOs. This costing process will quantify the resource and associated unit costs required to deliver each intervention step, organized in standard expenditure categories—personnel, supplies, equipment, services (e.g. electricity), space, and overhead. Costs will be allocated to each intervention step to the extent possible and review of the division of shared resources and staff time, noting and reporting uncertainties in these divisions. Information required to determine costs will be obtained through examination of expenditure records, discussion with program managers and staff including pharmacy, care delivery labs and observation of service delivery for a sample of patients. Focused “time and motion” studies to allocate staff time across tasks within and outside the intervention will also be carried out to properly account for health care workers’ time devoted to the intervention. Donated and subsidized resources will be appraised at market value. We will assess costs from the societal perspective, i.e. including costs to patients and their family members in the form of out-of-pocket expenditures and also lost productivity. To assess costs incurred by patients, we will administer short questionnaires to patients selected for participation in the Aim 2 sub-sample at intervention and control facilities that elicit their expenditures for transportation to receive treatment and the value of the time lost in accessing care by clients and accompanying family members and time lost due to illness.

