11.2.2 Risk of HIV/Suspected TB disclosure

Given the sensitive and private nature of HIV care and suspected TB evaluation data of participants collected during implementation of research Aim 2, extra cautions will be put in place to ensure maintenance of privacy, confidentiality, and security of the data obtained during chart review. Only deidentified data will be collected and recorded, minimizing any likelihood of inadvertent disclosure during chart review. Data collection and storage procedures will include the use of encrypted, password-protected devices and servers.

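### The Aim 4 cost-effectiveness population is stated inconsistently, and the by-arm TB comparison among IPT starters cannot inform the effect on TB

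*Protocol*

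**What the plan says.** **Aim 4 population.** Protocol Section 3.2 states: "The study population for Aim 4 will be the sub-sample from Aim 2". The Aim 4 objective in Section 2 ends the same way: "we will estimate the cost and cost-effectiveness of SPIRIT vs. standard of care in our sampled population from Aim 2". Section 4 likewise attaches costing outcomes to the sub-sample of adults prescribed INH. Yet the Section 2 sentence opens: "Using effectiveness measures obtained in Aims 1 and 2, and standard time and motion and costing methods". Section 8.2 assesses costs in both Aim 1 arms. Section 8.4 lists program cost per person starting IPT, per person completing it and per TB case averted, and ties none of these to the sub-sample. SAP Section 1 says the cost-effectiveness plan is held elsewhere.

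**Who is in the sub-sample.** Protocol Sections 3.2, 6.1 and 6.5.3 describe 800 HIV-positive adults prescribed INH, 400 per arm. SAP Section 5 keeps 400 per arm, all IPT starters, at 16 Southwestern facilities.

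**TB.** Protocol Section 5.6.1 says: "We will compare these outcomes (IPT completion and TB incidence) by study arm, within the sub-sample described for Aim 2 (below". Section 6.5.2.2 adds: "The analysis of TB incidence in the sub-sample of Aim 2 will mirror the analysis of IPT completion". The same section also plans a TB comparison in all HIV-positive adults in care. SAP Section 3 analyses TB in everyone in active HIV care, and the SAP specifies no by-arm TB comparison in the sub-sample.

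**Patient costs.** Section 8.1 takes a societal perspective and says: "we will administer short questionnaires to patients selected for participation in the Aim 2 sub-sample at intervention and control facilities". Section 11.2.2 says of the Aim 2 chart review: "Only deidentified data will be collected and recorded". The consent list in Section 11.2.1 covers DHOs and their TB staff, frontline providers and District Health Team members. It lists no patients.

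**The concern.** A sample made up only of IPT starters cannot show how many more people started IPT. Cost per initiation is the first Aim 4 outcome, so the stated population does not fit it.

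The same selection affects TB. SPIRIT is meant to reduce TB largely by getting more people onto IPT. Comparing TB between arms only among those who started removes that route and conditions on an event that the intervention is designed to change. Starters in the two arms may also differ in who was selected for treatment. A near-empty comparison of this kind could be reported as no effect on TB when it never tested the effect of raising uptake.

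**Working it through.** **1. Initiations inside the sub-sample.** The numbers are fixed by sampling at 400 and 400, so the increment is 400 − 400 = 0. An average cost per initiation computed there would divide by a sampling quota, not by an outcome of the trial.

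**2. Reproducing the protocol's TB figures (Section 6.5.2.2).** Inputs are 200 cases per 100,000 person-years, 10% completion, 40% efficacy and two years.
- Control cumulative incidence: 1 − exp[−2 × 0.002 × (1 − 0.10 × 0.40)] = 0.383%. The protocol states about 0.38%.
- Groups per arm, from the matched-pair cluster formula for proportions: c = 2 + (z_α/2 + z_β)² × [p0(1−p0)/m + p1(1−p1)/m + k_m²(p0² + p1²)] / (p0 − p1)².
- With p0 = 0.0038, p1 = 0.6 × 0.0038 = 0.00228, m = 2800, k_m = 0.2, two-sided 0.05 and 80% power, c = 12.02. The protocol assumes 12, so its 40% detectable reduction reproduces. (The trial has 7 groups per arm, which is a separate matter.)

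**3. Expected TB cases in the sub-sample, per arm.** Cases = 400 × 0.002 × years × (1 − 0.40 × proportion completing). The documents give no TB follow-up time for the sub-sample, so 9 months (the completion window) to 2 years is assumed. The lower completion value, 44%, is the control assumption in Section 6.5.2.1. The upper value is 100%.

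| Follow-up | 100% completing | 44% completing |
|---|---|---|
| 9 months | 0.36 | 0.49 |
| 1 year | 0.48 | 0.66 |
| 2 years | 0.96 | 1.32 |

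The Poisson chance of no case at all in an arm runs from exp(−0.36) = 70% to exp(−1.32) = 27%. The standard-of-care rate is applied to IPT starters, which is also an assumption. At an assumed 1,000 per 100,000 over two years, the count is 400 × 0.01 × 2 × 0.6 = 4.8 with everyone protected and 8.0 with no one protected, which is still few.

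**4. What a sub-sample comparison could pick up.** Leaving aside differences in who starts, the main remaining route is completion. Section 6.5.2.1 plans for 44% against a 40% relative increase, 1.4 × 44% = 61.6%. Expected cases averted over two years are 400 × 0.002 × 2 × 0.40 × (0.616 − 0.44) = 0.11. Even for a 40% TB reduction, power with 400 per arm is about 5–6% by a normal approximation that ignores clustering and is itself rough at these counts.

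**5. The population alternative.** At 2800 patients per group and 0.38%, seven control groups give 7 × 2800 × 0.0038 = 74 expected cases.

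**6. Patient costs.** Section 8.1 needs contact with sub-sample patients. Sections 6.1 and 11.2.2 describe de-identified record review, and Section 11.2.1 provides no patient consent. SAP Section 5 lists the variables recorded for the sub-sample, and none is a cost item. These texts do not fit together.

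**The case against.** The strongest reply is that the Aim 4 sentence already names Aims 1 and 2 as its sources of effectiveness. Aim 1 supplies initiations, and Aim 2 includes TB in the whole in-care population. The ratios in Section 8 are worded as program cost per person starting or completing, not as incremental ratios within the sub-sample. In Section 8 the sub-sample is named only for the patient questionnaires. Section 6.5.2.2 labels the target of the sub-sample TB analysis as IPT-prescribed persons. The economic analysis plan is not among these documents.

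Much of this stands. A reader might infer that cost per initiation is undefined, or that TB cases averted would rest on about one case per arm. The documents do not support either reading, because population sources for both quantities are named. A reader might also infer that sub-sample patients cannot be interviewed. That does not follow: Section 8.1 places the questionnaires at facilities, and recording de-identified chart data does not rule out a consented interview.

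The reply does not remove the conflict. Section 3.2, Section 4 and the end of the Section 2 sentence all place Aim 4 in the sub-sample, while the start of that sentence points elsewhere. It also does not rescue the sub-sample TB comparison, which correct labelling leaves with too few cases and without the initiation pathway.

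**Conclusion.** The concern holds as an unreconciled Aim 4 population plus one uninformative comparison.

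- **Aim 4.** If the stated population is followed, incremental initiations are zero by design and TB cases averted exclude the effect of higher initiation. If the opening of the objective is followed, both can be estimated. The protocol should say which applies. The separate economic plan may already do so, but it cannot be checked here.
- **Sub-sample TB.** About 0.4 to 1.3 cases are expected per arm. This rests on the protocol's rate and efficacy and on three assumptions: follow-up of 9 months to 2 years, 44–100% completion, and the standard-of-care rate applied to starters. The comparison cannot inform the effect on TB, even at a five-fold higher rate.
- **Patient costs.** Sections 8.1, 6.1, 11.2.1 and 11.2.2 conflict and need reconciling. This does not by itself require giving up the societal perspective.

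Secondary aims are affected. The primary endpoint and the population TB analysis are not.

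**What to change.** 1. **Sections 2 (Aim 4), 3.2 and 4:** state that incremental initiations come from the Aim 1 arm contrast and TB cases averted from the population TB contrast. Use the sub-sample only for completion and, if feasible, patient costs.
2. **Align costs and denominators.** Aim 1 counts adults at two clinics per district, the SAP TB outcome covers all persons in care across the district, and training, SMS and meeting costs are incurred for whole districts. State the common population for each ratio and any scaling assumption.
3. **Sections 5.6.1 and 6.5.2.2:** replace the between-arm TB comparison in the sub-sample with descriptive counts, and make the population analysis the only TB comparison. The SAP is already consistent with this.
4. **Sections 8.1, 6.1, 11.2.1 and 11.2.2:** either add patient consent for the cost questionnaires, or state that patient costs are not measured directly and narrow the perspective. The first needs ethics approval and fieldwork. The second gives up measured patient costs. The choice is the sponsor's.

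Items 1 to 3 are wording changes that use outcomes already planned. What is lost is a comparison with almost no information.
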